3. Background & Significance: Hearing loss affects millions of Americans and is a significant public health concern in the United States.^{8,9} The prevalence of hearing loss increases with increasing age.² In fact, data from National Health and Nutrition Examination Survey suggests that 10.5% of adults aged 55 to 64 years have hearing loss sufficiently disabling to warrant amplification. These prevalence rates increase to 25% for those 65 to 74 years and 50% for those 75+ years of age.¹⁰ The primary complaint of listeners with hearing loss, and older listeners with hearing loss in particular, is the reduced ability to understand speech, especially in background noise such as at parties or restaurants.^{11,12} This leads to difficulties with communication function in daily life.¹³⁻¹⁷ If left untreated, hearing loss has been shown to be associated with increased risk of dementia and cognitive decline,¹⁸⁻²² increased odds of falls,^{23,24} depression,^{16,25,26} social isolation,^{16,27,28} poor physical functioning,²⁹ lower levels of physical activity,³⁰ and reduced quality of life.^{8,16,31-35} Hearing loss also is associated with underemployment and economic burden.³⁶⁻³⁸ Hearing loss can even negatively affect significant others and care providers of affected individuals (i.e., third-party disability).^{35,39-43} Hearing aids are the primary intervention option for hearing loss, especially for degrees of hearing loss in the mild to moderate range which is the range most associated with ARHL.^{44,45} Hearing aids have been shown to be beneficial in terms of improved speech perception and communication function,⁴⁶⁻⁴⁹ reduced psychosocial implications of hearing loss,⁵⁰⁻⁵² improved health- and hearing-related quality of life,^{31-33,47,48} reduced impact on significant others (or reduced third-party disability),^{39,53} and reduced Medicare spending.⁵⁴ Hearing aid benefit also has been shown in those with mild hearing loss.^{47,55} Nascent reports suggest that treatment of hearing loss through hearing aids may even slow cognitive decline.⁵⁶⁻⁵⁹ Long-term benefit of hearing aid use also has been demonstrated.^{52,60,61} The recommendation for bilateral hearing aids for the treatment of bilateral hearing loss is considered the norm in the profession, unless there is a specific contradiction for bilateral amplification.^{5,62} In fact, clinical practice guidelines state that bilateral hearing aid fittings are recommended for *most* patients with bilateral hearing loss and that one hearing aid would only be recommended in circumstances related to patient need, hearing asymmetry, or personal reasons such as cosmetics or financial.³ The benefit of bilateral hearing aids over a unilateral hearing aid has been demonstrated in specific contexts such as with speech understanding in complex noise (e.g., spatially separated), cognitively demanding

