This study will be conducted at Duke and Vanderbilt, with Duke functioning as the coordinating center and single IRB. Our aim is to compare unilateral versus bilateral fittings of commercially-available hearing aids. Phonak® (our industry partner) agreed to extend the trial period from 45 days to 180 days to ensure subjects have adequate time to complete the study, and at a modestly reduced rate. Subjects will pay out-of-pocket for the devices and care and/or use their insurance benefits if applicable.

Phase 1:

Screening Visit: Patients undergoing routine comprehensive audiometric evaluation by a site clinical audiologist for a hearing concern will be considered for the study. The data from these routine, best practices visits will be extracted from the medical record and audiometric databases if the patient agrees to enroll in the study.

Baseline Visit: The study coordinator will screen the subject for inclusion in the study and obtain informed consent. Questionnaires including MOCA, APHAB, GHABP, HHIE, SSQ, TFI, and ECHO will be completed via REDCap electronically and the responses blinded to the remaining study staff. Participants will be asked to complete a demographic intake form that includes collection of socioeconomic data (salary, education, marital status, living arrangements). In addition, participants will be asked to answer a series of questions related to the use of facemasks during COVID19. The baseline study auditory testing (research variables) will be conducted by the research audiologist. Eligible subjects will be randomly assigned to one of the two treatment groups in a 1:1 ratio via a random-number generator. The unilateral fitting group will choose the ear in which they want fitted. If they do not have a preference, then they will be further assigned the ear in which the hearing aid will be fitted with a 1:1 ratio.

Patients will be given a purchase agreement for the hearing aids which lists the price of the hearing aids, discount received, fitting fee, and details on refunds should they want to return the hearing aids.

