Speech and Noise Test	
Baseline (unaided) and 3-months (aided)
 
Speech and noise 0 degrees (collocated)
 
Speech left, noise right
 
Noise left, speech right
	
Baseline:
 
sin_collocated_base sin_right_base sin_left_base
 
3-Months:
 
sin_collocated_3m sin_right_3m sin_left_3m
 
Change:
 
sin_collocated_change sin_r_change sin_l_change
 
May also want change scores for speech to aided side and speech to unaided side
	
Continuous
 
Change scores: 3m-baseline for each of collocated, speech left/noise right, noise left/speech right
 
Positive values for unaided/aided variables indicate speech is louder than noise; negative indicate speech is under the noise
 
For unilateral assigned, also have speech to aided side (advantage) and speech to unaided side (disadvantage).
 
Speech to aided (advantage):
 
 • If assigned R, this is noise left, speech right

			
 • If assigned L, this is speech left, noise right 
Speech to unaided (disadvantage):
 
 • If assigned R, this is speech left, noise right • If assigned L, this is noise left, speech right 
Lower scores are better

Auditory Working Memory	
Unaided and Aided (3 months)
 
Recognition, judgement, recall
	
Change scores: warrm_recog_change warrm_recall_change
 
Baseline: warrm_recog_base warrm_recall_base warrm_judge_base
 
3-Months: warrm_recog_3m warrm_recall_3m warrm_judge_3m
	
Continuous
 
Sum questions 2-6 for each tasks (recognition, judgement, recall) separately and get a % correct (out of 20)
 
Construct change scores as difference between 3 months and baseline for recognition and recall.
 
Judgement is more of a sanity check (<90% means they probably aren't engaged)
 
Higher scores are better

Hours of Hearing Aid Use	
Multiple time periods (every scheduled visit and unscheduled follow ups)
 
Only reporting 3-month values here
 
Right and left ears separately
	
Right ear: r_avg_hrs_3m r_avg_hrs_3m_na (if right HA is NA)
 
Left ear: l_avg_hrs_3m l_avg_hrs_3m_na
	
How many hours on average the right/left HA was worn.
 
NA variables: value of 1 if that HA was NA

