4.1 Aim: compare all outcomes between the two arms

Compare the outcomes between the two arms (bilateral hearing aid and unilateral hearing aid) at 3 months.

Analysis: This will be reported for patients who have 3-month scores ("completers"). The primary analysis will be performed using either t-tests or Kruskal Wallis tests depending on whether or not the outcome

distributions appear to be normally distributed. The total score for each survey at 3 months or the benefit score will be used as the outcomes. For GHABP, we will compare the four standard questions (averaged and standardized) for the 4 standard scenarios between the two arms at 3 months for patients who answer "yes" to the first question (if the scenario happens).

The null hypothesis is that the means of the outcomes for the two treatment groups are the same.

$$H_0: \mu_{unilateral} = \mu_{bilateral}$$

Table 1: Distributions of 3-Month Outcomes or Benefit Scores by Assigned Treatment Group

	Unilateral (N=XXX)	Bilateral (N=XXX)	P-Value*
GHABP Aided: In this situation, what proportion of the time do you wear your hearing aid?			XXX
N	XXX	XXX	
Missing	XXX	XXX	
Mean (SD)	XXX (XXX)	XXX (XXX)	
Median	XXX	XXX	
Q1, Q3	XXX, XXX	XXX, XXX	
Range	XXX - XXX	XXX - XXX	
GHABP Aided: In this situation, how much does your hearing aid help you?			XXX
N	XXX	XXX	
Missing	XXX	XXX	
Mean (SD)	XXX (XXX)	XXX (XXX)	
Median	XXX	XXX	
Q1, Q3	XXX, XXX	XXX, XXX	
Range	XXX - XXX	XXX - XXX	
GHABP Aided: In this situation, with your hearing aid, how much difficulty do you now have?			XXX
N	XXX	XXX	
Missing	XXX	XXX	
Mean (SD)	XXX (XXX)	XXX (XXX)	
Median	XXX	XXX	
Q1, Q3	XXX, XXX	XXX, XXX	
Range	XXX - XXX	XXX - XXX	
GHABP Aided: For this situation, how satisfied are you with your hearing aid?			XXX
N	XXX	XXX	
Missing	XXX	XXX	
Mean (SD)	XXX (XXX)	XXX (XXX)	
Median	XXX	XXX	
Q1, Q3	XXX, XXX	XXX, XXX	
Range	XXX - XXX	XXX - XXX	
SADL Global Score			XXX
N	XXX	XXX	

Missing	XXX	XXX
Mean (SD)	XXX (XXX)	XXX (XXX)
Median	XXX	XXX
Q1, Q3	XXX, XXX	XXX, XXX
Range	XXX - XXX	XXX - XXX
HHI-E Change Score		XXX
N	XXX	XXX
Missing	XXX	XXX
Mean (SD)	XXX (XXX)	XXX (XXX)
Median	XXX	XXX
Q1, Q3	XXX, XXX	XXX, XXX
Range	XXX - XXX	XXX - XXX
IOI-HA Total Score		XXX
N	XXX	XXX
Missing	XXX	XXX
Mean (SD)	XXX (XXX)	XXX (XXX)
Median	XXX	XXX
Q1, Q3	XXX, XXX	XXX, XXX
Range	XXX - XXX	XXX - XXX
SSQ Change Score		XXX
N	XXX	XXX
Missing	XXX	XXX
Mean (SD)	XXX (XXX)	XXX (XXX)
Median	XXX	XXX
Q1, Q3	XXX, XXX	XXX, XXX
Range	XXX - XXX	XXX - XXX

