Speech and Noise Test: 0 Degrees (Co-located) Change Score		XXX
N	XXX	XXX
Missing	XXX	XXX
Mean (SD)	XXX (XXX)	XXX (XXX)
Median	XXX	XXX
Q1, Q3	XXX, XXX	XXX, XXX
Range	XXX - XXX	XXX - XXX
Auditory Working Memory - Recognition Change Score		XXX
N	XXX	XXX
Missing	XXX	XXX
Mean (SD)	XXX (XXX)	XXX (XXX)
Median	XXX	XXX
Q1, Q3	XXX, XXX	XXX, XXX
Range	XXX - XXX	XXX - XXX
Auditory Working Memory - Recall Change Score		
N	XXX	XXX
Missing	XXX	XXX
Mean (SD)	XXX (XXX)	XXX (XXX)
Median	XXX	XXX
Q1, Q3	XXX, XXX	XXX, XXX
Range	XXX - XXX	XXX - XXX

Average Hours of Hearing Aid Use**At 3-Month Visit: Right Ear**

XXX

N	XXX	XXX
Missing	XXX	XXX
Mean (SD)	XXX (XXX)	XXX (XXX)
Median	XXX	XXX
Q1, Q3	XXX, XXX	XXX, XXX
Range	XXX - XXX	XXX - XXX

Average Hours of Hearing Aid Use

XXX

At 3-Month Visit: Left Ear

N	XXX	XXX
Missing	XXX	XXX
Mean (SD)	XXX (XXX)	XXX (XXX)
Median	XXX	XXX
Q1, Q3	XXX, XXX	XXX, XXX
Range	XXX - XXX	XXX - XXX

*T-test/Kruskal Wallis

We will create boxplots or other figures displaying the distributions of these outcomes by randomization. These figures may supplement or replace Table 1 above.

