4.2 Aim: descriptive tables/plots for additional variables

Analysis: we will describe or plot the distributions of additional variables at baseline, hearing aid fit, or 3 month visit as appropriate by assigned treatment. For GHABP, the two unaided (baseline) questions and the one aided (3-month) question (averaged and standardized) will only include patients who answered "yes" to the first question (if the scenario happens). These will be reported across the 4 standard scenarios.

Table 2: Distributions of Clinical Variables by Assigned Treatment

	Unilateral (N=XXX)	Bilateral (N=XXX)
GHABP Unaided: How much difficulty do you have in this situation?		
N	XXX	XXX
Missing	XXX	XXX
Mean (SD)	XXX (XXX)	XXX (XXX)
Median	XXX	XXX
Q1, Q3	XXX, XXX	XXX, XXX
Range	XXX - XXX	XXX - XXX
GHABP Unaided: How much does any difficulty in this situation worry, annoy or upset you?		
N	XXX	XXX
Missing	XXX	XXX
Mean (SD)	XXX (XXX)	XXX (XXX)
Median	XXX	XXX
Q1, Q3	XXX, XXX	XXX, XXX
Range	XXX - XXX	XXX - XXX

GHABP Aided: In this situation, with your hearing aid, how much does any difficulty in this situation worry, annoy, or upset you?

N	XXX	XXX
Missing	XXX	XXX
Mean (SD)	XXX (XXX)	XXX (XXX)
Median	XXX	XXX
Q1, Q3	XXX, XXX	XXX, XXX
Range	XXX - XXX	XXX - XXX

ECHO Global Score (Baseline)

N	XXX	XXX
Missing	XXX	XXX
Mean (SD)	XXX (XXX)	XXX (XXX)
Median	XXX	XXX
Q1, Q3	XXX, XXX	XXX, XXX
Range	XXX - XXX	XXX - XXX

ECHO Positive Effect Subscale (Baseline)

N	XXX	XXX
Missing	XXX	XXX
Mean (SD)	XXX (XXX)	XXX (XXX)
Median	XXX	XXX
Q1, Q3	XXX, XXX	XXX, XXX
Range	XXX - XXX	XXX - XXX

ECHO Service Cost Subscale (Baseline)

N	XXX	XXX
Missing	XXX	XXX
Mean (SD)	XXX (XXX)	XXX (XXX)
Median	XXX	XXX
Q1, Q3	XXX, XXX	XXX, XXX
Range	XXX - XXX	XXX - XXX

ECHO Negative Features Subscale (Baseline)

N	XXX	XXX
Missing	XXX	XXX
Mean (SD)	XXX (XXX)	XXX (XXX)
Median	XXX	XXX
Q1, Q3	XXX, XXX	XXX, XXX
Range	XXX - XXX	XXX - XXX

ECHO Personal Image Subscale (Baseline)

N	XXX	XXX
Missing	XXX	XXX
Mean (SD)	XXX (XXX)	XXX (XXX)
Median	XXX	XXX
Q1, Q3	XXX, XXX	XXX, XXX
Range	XXX - XXX	XXX - XXX

SADL Positive Effect Subscale (3 Months)

N	XXX	XXX
Missing	XXX	XXX
Mean (SD)	XXX (XXX)	XXX (XXX)
Median	XXX	XXX
Q1, Q3	XXX, XXX	XXX, XXX
Range	XXX - XXX	XXX - XXX

SADL Service Cost Subscale (3 Months)

N	XXX	XXX
Missing	XXX	XXX
Mean (SD)	XXX (XXX)	XXX (XXX)
Median	XXX	XXX
Q1, Q3	XXX, XXX	XXX, XXX
Range	XXX - XXX	XXX - XXX

SADL Negative Features**Subscale (3 Months)**

N	XXX	XXX
Missing	XXX	XXX
Mean (SD)	XXX (XXX)	XXX (XXX)

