Subscale (Baseline)

N	XXX	XXX
Missing	XXX	XXX
Mean (SD)	XXX (XXX)	XXX (XXX)
Median	XXX	XXX
Q1, Q3	XXX, XXX	XXX, XXX
Range	XXX - XXX	XXX - XXX

SSQ Qualities of Hearing

Subscale (3-Month)

N	XXX	XXX
Missing	XXX	XXX
Mean (SD)	XXX (XXX)	XXX (XXX)

Median	XXX	XXX
Q1, Q3	XXX, XXX	XXX, XXX
Range	XXX - XXX	XXX - XXX
Binaural Loudness Summation:		
Right (Baseline)		
N	XXX	XXX
Missing	XXX	XXX
Mean (SD)	XXX (XXX)	XXX (XXX)
Median	XXX	XXX
Q1, Q3	XXX, XXX	XXX, XXX
Range	XXX - XXX	XXX - XXX
Binaural Loudness Summation:		
Left (Baseline)		
N	XXX	XXX
Missing	XXX	XXX
Mean (SD)	XXX (XXX)	XXX (XXX)
Median	XXX	XXX
Q1, Q3	XXX, XXX	XXX, XXX
Range	XXX - XXX	XXX - XXX
Binaural Loudness Summation:		
Both (Baseline)		
N	XXX	XXX
Missing	XXX	XXX
Mean (SD)	XXX (XXX)	XXX (XXX)
Median	XXX	XXX
Q1, Q3	XXX, XXX	XXX, XXX
Range	XXX - XXX	XXX - XXX
Dichotic Digits: Right Ear Directed (Baseline)		
N	XXX	XXX
Missing	XXX	XXX
Mean (SD)	XXX (XXX)	XXX (XXX)
Median	XXX	XXX
Q1, Q3	XXX, XXX	XXX, XXX
Range	XXX - XXX	XXX - XXX
Dichotic Digits: Left Ear Directed (Baseline)		
N	XXX	XXX
Missing	XXX	XXX
Mean (SD)	XXX (XXX)	XXX (XXX)
Median	XXX	XXX
Q1, Q3	XXX, XXX	XXX, XXX
Range	XXX - XXX	XXX - XXX
Dichotic Digits: Free Recall Both (Baseline)		
N	XXX	XXX
Missing	XXX	XXX
Mean (SD)	XXX (XXX)	XXX (XXX)
Median	XXX	XXX
Q1, Q3	XXX, XXX	XXX, XXX

Range	XXX - XXX	XXX - XXX
Dichotic Digits: Free Recall Right (Baseline)		
N	XXX	XXX
Missing	XXX	XXX
Mean (SD)	XXX (XXX)	XXX (XXX)
Median	XXX	XXX
Q1, Q3	XXX, XXX	XXX, XXX
Range	XXX - XXX	XXX - XXX
Dichotic Digits: Free Recall Left (Baseline)		
N	XXX	XXX
Missing	XXX	XXX
Mean (SD)	XXX (XXX)	XXX (XXX)
Median	XXX	XXX
Q1, Q3	XXX, XXX	XXX, XXX
Range	XXX - XXX	XXX - XXX
Speech and Noise Test: 0 Degrees (Co-located) Score (Baseline)		
N	XXX	XXX
Missing	XXX	XXX
Mean (SD)	XXX (XXX)	XXX (XXX)
Median	XXX	XXX
Q1, Q3	XXX, XXX	XXX, XXX
Range	XXX - XXX	XXX - XXX
Speech and Noise Test: 0 Degrees (Co-located) Score (3-Month)		
N	XXX	XXX
Missing	XXX	XXX
Mean (SD)	XXX (XXX)	XXX (XXX)
Median	XXX	XXX
Q1, Q3	XXX, XXX	XXX, XXX
Range	XXX - XXX	XXX - XXX
Speech and Noise Test: Speech Left, Noise Right Score (Baseline)		
N	XXX	XXX
Missing	XXX	XXX
Mean (SD)	XXX (XXX)	XXX (XXX)
Median	XXX	XXX
Q1, Q3	XXX, XXX	XXX, XXX
Range	XXX - XXX	XXX - XXX
Speech and Noise Test: Speech Left, Noise Right Score (3-Month)		
N	XXX	XXX
Missing	XXX	XXX
Mean (SD)	XXX (XXX)	XXX (XXX)

Median	XXX	XXX
Q1, Q3	XXX, XXX	XXX, XXX
Range	XXX - XXX	XXX - XXX
Speech and Noise Test: Speech Left, Noise Right Change Score		

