N	XXX	XXX
Missing	XXX	XXX
Mean (SD)	XXX (XXX)	XXX (XXX)
Median	XXX	XXX
Q1, Q3	XXX, XXX	XXX, XXX
Range	XXX - XXX	XXX - XXX
Speech and Noise Test: Noise Left, Speech Right Score (Baseline)		
N	XXX	XXX
Missing	XXX	XXX
Mean (SD)	XXX (XXX)	XXX (XXX)
Median	XXX	XXX
Q1, Q3	XXX, XXX	XXX, XXX
Range	XXX - XXX	XXX - XXX
Speech and Noise Test: Noise Left, Speech Right Score (3-Month)		
N	XXX	XXX
Missing	XXX	XXX
Mean (SD)	XXX (XXX)	XXX (XXX)
Median	XXX	XXX
Q1, Q3	XXX, XXX	XXX, XXX
Range	XXX - XXX	XXX - XXX
Speech and Noise Test: Noise Left, Speech Right Change Score		
N	XXX	XXX
Missing	XXX	XXX
Mean (SD)	XXX (XXX)	XXX (XXX)
Median	XXX	XXX
Q1, Q3	XXX, XXX	XXX, XXX
Range	XXX - XXX	XXX - XXX
Auditory Working Memory - Recognition Score (Baseline)		
N	XXX	XXX
Missing	XXX	XXX
Mean (SD)	XXX (XXX)	XXX (XXX)
Median	XXX	XXX
Q1, Q3	XXX, XXX	XXX, XXX
Range	XXX - XXX	XXX - XXX
Auditory Working Memory - Recognition Score (3-Month)		
N	XXX	XXX
Missing	XXX	XXX
Mean (SD)	XXX (XXX)	XXX (XXX)

Median	XXX	XXX
Q1, Q3	XXX, XXX	XXX, XXX
Range	XXX - XXX	XXX - XXX
Auditory Working Memory - Recall Score (Baseline)		
N	XXX	XXX
Missing	XXX	XXX
Mean (SD)	XXX (XXX)	XXX (XXX)
Median	XXX	XXX
Q1, Q3	XXX, XXX	XXX, XXX
Range	XXX - XXX	XXX - XXX
Auditory Working Memory - Recall Score (3-Month)		
N	XXX	XXX
Missing	XXX	XXX
Mean (SD)	XXX (XXX)	XXX (XXX)
Median	XXX	XXX
Q1, Q3	XXX, XXX	XXX, XXX
Range	XXX - XXX	XXX - XXX
Auditory Working Memory - Judgement Score (Baseline)		
N	XXX	XXX
Missing	XXX	XXX
Mean (SD)	XXX (XXX)	XXX (XXX)
Median	XXX	XXX
Q1, Q3	XXX, XXX	XXX, XXX
Range	XXX - XXX	XXX - XXX
Auditory Working Memory - Judgement Score (3-Month)		
N	XXX	XXX
Missing	XXX	XXX
Mean (SD)	XXX (XXX)	XXX (XXX)
Median	XXX	XXX
Q1, Q3	XXX, XXX	XXX, XXX
Range	XXX - XXX	XXX - XXX

We will plot the average absolute difference between target and output at each frequency for each ear by assigned hearing aid configuration for both the hearing aid fit and 3-month visits (with visits either grouped together in the same plot or plotted separately). We will also do this for the average difference between MPO and UCL at each frequency.

5 Future Plans

There are additional items we may wish to explore in the future, at which point a new SAP will be developed. Ideas include looking at:

- Additional GHABP measures
- EMA surveys
- Mask questions

- Additional hearing aid hours of use
- Unscheduled visits

Statistical Analysis Plan (SAP) – Secondary (6-Month) Outcomes and Descriptives

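### The between-arm table of the 3-month SAP tests only co-located speech-in-noise; the two separated conditions are described by physical side, which mixes aided-side and unaided-side listening in the unilateral arm.

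*SAP*

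**What the plan says.** Protocol section 2 makes the comparison of performance outcomes its first secondary objective. Protocol section 3 says that bilateral benefit has been demonstrated in particular contexts, "such as with speech understanding in complex noise (e.g., spatially separated").

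In the secondary (3-month) SAP, section 1.1 says that all outcomes will be compared between the arms. Section 3.1 lists the Speech and Noise Test as an outcome with three conditions: co-located, speech left with noise right, and noise left with speech right. Each has a change score. For unilateral patients the same row defines which separated condition is speech to the aided side (labelled an advantage) and which is speech to the unaided side (labelled a disadvantage). It then says only "May also want change scores for speech to aided side and speech to unaided side".

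Section 4.1 covers the formal comparison: "The primary analysis will be performed using either t-tests or Kruskal Wallis tests depending on whether or not the outcome" distributions look normal. Its Table 1 has a P-value column and one speech-in-noise row, "Speech and Noise Test: 0 Degrees (Co-located) Change Score".

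Section 4.2 is descriptive: "we will describe or plot the distributions of additional variables at baseline, hearing aid fit, or 3 month visit as appropriate by assigned treatment". Its Table 2 has no P-value column. It holds "Speech and Noise Test: Speech Left, Noise Right Change Score" and "Speech and Noise Test: Noise Left, Speech Right Change Score". No table or model uses the aided-side and unaided-side scores.

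On the fitted ear, Protocol section 4 (Baseline Visit) says: "The unilateral fitting group will choose the ear in which they want fitted". Patients without a preference are assigned an ear 1:1.

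**The concern.** There are two linked problems.

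First, the stated aim and the tables do not match. The separated change scores are listed as outcomes and all outcomes are to be compared, yet these scores are left out of the only table that compares. They are also the kind of setting in which the protocol says bilateral benefit has been seen. A null co-located result could then be read as showing no speech-in-noise advantage when the separated conditions were never tested.

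Second, the description that is planned does not line up with the treatment. In the speech-left row, a unilateral patient fitted on the left hears speech on the aided side, and one fitted on the right hears it on the unaided side. The row averages the two in proportions set mostly by patient preference. The left and right rows can then differ between arms simply because more people chose one ear.

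**Working it through.** **Inputs from the documents.** 350 planned (Protocol section 6), allocated 1:1 (Protocol section 4), so 350/2 = 175 per arm. The only power input anywhere is an APHAB SD of 25. Nothing is given for speech-in-noise, so there is no planned figure to reproduce.

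**Assumptions.** Effects in units of the within-condition SD (set to 1), two-sided 0.05, normal approximation, no dropout.

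**Notation.** Lower scores are better, so let a contrast be the unilateral minus the bilateral mean change; positive values favour bilateral. dU is the contrast with speech on the unilateral patient's unaided side, dA the contrast with speech on the aided side, and pL the share of the unilateral arm fitted on the left.

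**Step 1: what each Table 2 row shows.**
- Speech left: pL·dA + (1 − pL)·dU
- Speech right: (1 − pL)·dA + pL·dU

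Mixing also adds pL(1 − pL)(dU − dA)² to the unilateral arm's variance.

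**Step 2: size of the dilution.**
- pL = 0.5, dA = 0: both rows show 0.5·dU. With dU = 0.5 that is 0.25.
- pL = 0.5, dA = dU: both rows show dU, so there is no dilution.
- pL = 0.5, dA = −dU: both rows show 0.
- pL = 0.3, dU = 0.5, dA = 0: speech left is 0.7 × 0.5 = 0.35 and speech right is 0.3 × 0.5 = 0.15. The rows differ only through the ear mix.

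**Step 3: what is recoverable.** Adding the two rows gives dA + dU whatever pL is, because within a person left plus right equals aided plus unaided. The average over sides, (dA + dU)/2, can therefore be read from Table 2 if the same patients contribute to both rows. Its standard error cannot, because the within-person covariance is not reported. The separate values of dA and dU cannot be recovered.

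**Step 4: illustrative power at 175 per arm, pL = 0.5.** For a single row, the standard error is √[(2 + 0.25(dU − dA)²)/175]. For the within-person mean, the SD is √[(1 + r)/2] and the standard error √[(1 + r)/175]. With an assumed within-person correlation r = 0.4, the SD is √0.7 = 0.837 and the standard error √(1.4/175) = 0.0894. Power is Φ(contrast/SE − 1.96).

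| dU | dA | Contrast, row or mean | Power if one row were tested | Power, within-person mean |
|---|---|---|---|---|
| 0.5 | 0 | 0.25 | 63% | 80% |
| 0.5 | 0.25 | 0.375 | 94% | 99% |
| 0.3 | 0 | 0.15 | 29% | 39% |
| 0.3 | 0.15 | 0.225 | 56% | 71% |
| 0.3 | 0.3 | 0.30 | 80% | 92% |

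For dU = 0.5 and dA = 0, the power of the mean runs from 86% at r = 0.2 to 69% at r = 0.8. The mean has the same expected contrast as a row when the ear split is even; it gains only through its smaller SD. An unaided-side contrast against a bilateral comparator with SD 1 would have 99.7% power at dU = 0.5 and 80% at dU = 0.3, but it is a different estimand (see the objection).

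**The case against.** The strongest reply is that nothing planned is damaged. Table 2 is descriptive, so the single-row power figures belong to a test that the SAP does not propose. That stands. A reader might infer that the plan dilutes the effect the trial is about. It does not: the primary aim is the APHAB change score, and Protocol section 3 puts real-world outcomes ahead of laboratory ones. Secondary objective 1 is also served by the working-memory recognition and recall change scores, which are in Table 1.

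A reader might also infer that co-located noise is the condition least able to separate the arms. The protocol names separated noise as one context of demonstrated benefit; it does not rank co-located noise against it.

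Nor is the separated contrast cancelled outright, since the side average survives in the two rows. How much is lost depends on dA, which is unknown, although the SAP's advantage and disadvantage labels presuppose that the two sides differ.

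Finally, the most powerful option, speech to the unaided side, is the least secure. The bilateral arm has no unaided side, so the comparator has to be constructed. The fitted ear is mostly chosen by the patient, and Protocol section 5 allows up to (but not including) 20 dB asymmetry, so the unaided ear may systematically be the better or the poorer one. This also stands, and it is why that contrast should not be the tested one.

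The reply does not remove the mismatch between section 1.1 and Table 1, or the mixing in the rows.

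**Conclusion.** The point holds as a modest, inexpensive improvement to a secondary analysis. The text settles two facts: the separated change scores are listed outcomes that are not compared, and the left and right rows blend aided-side and unaided-side listening in the unilateral arm. The size is conditional. A row shows half of dU under an even split with dA = 0, and all of it when dA = dU. Every power figure rests on an assumed effect, correlation and ear split, with no dropout. The documents do not support reading this as a loss of power in a planned test or as a threat to the trial's main conclusion.

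**What to change.** 1. Add one row to Table 1 of the 3-month SAP: the within-person mean of the two separated change scores, tested in the same way as the other rows. It is defined identically in both arms, does not depend on which ear was fitted, and keeps the protection of randomisation. State that both separated scores are required at both visits.
2. In Table 2, replace or supplement the unilateral left and right rows with the speech-to-aided and speech-to-unaided change scores, using the definition already in section 3.1. Set them beside the bilateral arm's two-side mean. Label them supportive, because the ear is mostly patient-chosen and the bilateral arm has no unaided side.
3. Replace the optional wording in section 3.1 with a definite statement, so that section 1.1, section 3.1 and the tables agree.
4. Date the change in the activity log. The SAP version is 09.30.2024, the data pull 10.17.2024 and the analysis was due by December 31, 2024, so label the addition post hoc if outcome data have already been seen.

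The cost is SAP wording and light programming. The scores are collected and the fitted ear is recorded (section 3.2, Hearing Aid Fitting information). The downside is one more secondary test beside the 13 rows already in Table 1, for which this SAP states no multiplicity control.
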